mRS	Modified Rankin Score	Scale for measuring general neurological function. 0 No symptoms at all 1 No significant disability despite symptoms; able to carry out all usual duties and activities 2 Slight disability; unable to carry out all previous activities, but able to look after own affairs without assistance 3 Moderate disability; requiring some help, but able to walk without assistance 4 Moderately severe disability; unable to walk without assistance and unable to attend to own bodily needs without assistance 5 Severe disability; bedridden, incontinent and requiring constant nursing care and attention 6 Dead
NIHSS	National Institute of Health Stroke Scale	Method for quantifying neurologic deficits developed by the National Institutes of Health. It is used to assess the severity of a stroke.
PED	Pipeline Endovascular Device	Pipeline Endovascular Device

Abbreviation	Abbreviated Term	Definition
Primary Efficacy Endpoint	Complete aneurysm occlusion (defined as Raymond-Roy grade 1 ⁵⁵) without significant parent artery stenosis (\leq 50%) or retreatment of the target aneurysm 1-year post-procedure	The primary effectiveness endpoint assessed by: 
• Occlusion status: by a 3-member adjudicated read by the imaging Core Laboratory according to the Scale of Roy• Parent Artery stenosis: by the 3-member adjudicated read by the imaging Core Laboratory.• Retreatment: by the investigator reported events of retreatment.

Abbreviation	Abbreviated Term	Definition

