Subjects will be considered enrolled in the study once the patient has signed and dated the Informed Consent or DRF and the Pipeline™ Flex Embolization Device with Shield Technology™ is advanced into the micro catheter inside the patient. All enrolled subjects who underwent the study procedure and in whom an attempt to implant the device was made will be included in the analysis population.

A CEC will be in place for the study using a minimum of three physicians knowledgeable in the appropriate disciplines and medical specialties pertinent to the disease state being evaluated in this clinical study. This committee will be responsible for the review and adjudication to the study variables of all events identified in the CEC Charter/Manual of Operations.

The CEC will independently adjudicate to specified endpoint event definitions, event relatedness, event severity, and event outcomes.

The imaging core laboratory will be responsible for the qualitative image analysis to determine aneurysm occlusion, parent artery stenosis, and device migration. An imaging protocol will be provided to the site.

Pre-Specified Study Endpoints:

The pre-specified study endpoints and analysis listed here are the primary body of data that will be collected, analyzed, and summarized in a series of tables, lists, and graphs as part of the final report for this study. Other analysis will be conducted as part of the final report but these are the core set of analyses that will constitute the foundation of the clinical study report.

Primary endpoints:

Safety:

- Occurrence of major stroke in the territory supplied by the treated artery or neurological death post-procedure (1-year)

Effectiveness:

- Complete aneurysm occlusion (defined as Raymond-Roy grade 1) without significant parent artery stenosis ($\leq 50\%$) or retreatment of the target aneurysm post-procedure (1-year)

Secondary endpoints:

Safety:

- Occurrence of major stroke in the territory supplied by the treated artery or neurological death at 30 days post-procedure due to procedural complications
- Delayed intracerebral hemorrhage > 30 days post-procedure

Effectiveness:

- Device deployment success rate at the target site

Additional Safety Analyses:

- [REDACTED]
- [REDACTED]

- [REDACTED]
 - [REDACTED]
 - [REDACTED]

Additional Effectiveness Analyses:

- [REDACTED]
 - [REDACTED]
 - [REDACTED]
- [REDACTED]
- [REDACTED]
- [REDACTED]
- [REDACTED]
- [REDACTED]

Study Procedure:

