Subjects will be considered enrolled in the study once the patient has signed and dated the Informed Consent or DRF and the Pipeline™ Flex Embolization Device with Shield Technology™ is advanced into the micro catheter inside the patient. Per each site’s standard of care procedure, at screening, each patient can undergo a neurologic examination and assessment using the mRS and NIHSS, blood draw for hematocrit, platelet count, platelet function testing, serum creatinine, and a pregnancy test (if applicable). Pertinent medications taken by the study participant starting on the day of study procedure were collected while for platelet reactivity start date can also be > 30 days before procedure (in case patient was already under antiplatelet, including anticoagulants and antiplatelet therapy). Subjects will be assessed and documented at baseline. Patient eligibility assessment is to be performed based on data available to the investigator at the time of screening. Patient will be considered a screen failure if:

- The patient signs the informed consent or DRF but fails to meet study inclusion/exclusion criteria during the screening and baseline phase.
- The patient signs the informed consent or DRF, meets the study inclusion/exclusion criteria but an attempt to implant the Pipeline™ Flex Embolization Device with Shield Technology™ is not performed.

The investigator will assess device occlusion, device placement and overall status of the aneurysm. At the investigator’s discretion, the target IA may be retreated at any time during the study. In such situations, the date of the initial procedure (and not the date of the retreatment) will be considered Day 0.

If the target IA undergoes an attempted deployment with the Pipeline™ device with Shield Technology™ but is not implanted or receives an alternate treatment (e.g., coils), the patient is considered an implant failure and will be followed up until hospital discharge. However, if the target IA does not undergo an attempted deployment with the Pipeline™ device with Shield Technology™ and is not treated or receives an alternate treatment (e.g., coils) during the initial procedure, the patient is considered a screen failure and no further follow up is required.

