The non-ICA is a subset of the ITT population including only those subjects in whom the Pipeline™ device with Shield Technology™ was implanted in the arterial vessels other than those specified in the ICA population.

6. Determination of Sample Size

No formal estimates were prepared for examining the individual variables. However, the incidence of certain events will be examined relative to the thresholds used in research treating a similar population. Device outcomes variables recorded on a dichotomous scale will be summarized using a 2-sided 95% Clopper-Pearson exact binomial confidence interval. The upper and lower bounds of the confidence interval will be examined relative to results in the peer-reviewed literature and studies using the

Pipeline device without the Shield Technology™. Specifically, the incidence at 1 year post-procedure of a major stroke in the territory supplied by the treated artery or neurological death will be examined relative to an a priori threshold of 15%. The incidence at 1 year post-procedure of aneurysm occlusion without significant parent artery stenosis will be examined relative to an a priori threshold of 50%.

7. Statistical Methods

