- Number of times re-sheathing was attempted. The count (0, 1, 2, or >2) comes directly from the clinical case report form.
- Entire IA neck covered by the study device. Complete neck coverage has a binary outcome and comes directly from the core lab
- Side branches covered by the study device. Complete side branch coverage has a binary outcome and comes directly from the core lab
- Post-deployment stasis (complete, significant, or no disruption of inflow jet); evaluated as 1 of 3 possible states, comes directly from the core lab
- Target aneurysm partially thrombosed; a binary endpoint that comes directly from the core lab
- Percentage of target aneurysm thrombosis; a continuous endpoint that comes directly from the core lab
- Achievement of wall apposition; a binary endpoint that comes directly from the core lab.

The duration of the procedure (min) will also be summarized and presented using descriptive statistics.

The supportive data for these series of tables will be presented in a listing entitled *Device and Peri-Procedure Analyses*. This listing will be sorted by patient number.

Overall Summary of the Post-Procedure Variables Recorded Over Time

The post-procedure analyses will be summarized for the following 5 time points: Post-Procedure Discharge, 1 Month Post-Procedure, 3 Months Post-Procedure, 6 Months Post-Procedure, and 1 Year Post-Procedure. The following 10 separate parameters will be summarized:

- Aneurysm occlusion (Class 1: Complete obliteration, Class 2: Residual neck, or Class 3: Residual Aneurysm), derived from the post-procedure imaging adjudicated by core lab.
- Modified Rankin Scale (mRS). The mRS score at 1 year will be dichotomized (>2 vs. ≤ 2) and summarized using counts, percentages, and 2-sided 95% exact binomial confidence intervals.
- NIH Stroke Scale (NIHSS)
- Platelet reactivity testing
- Change in antiplatelet therapy because of the platelet reactivity testing
- Retreatment of the target aneurysm
- Major stroke in the territory supplied by the treated artery or neurological death at 30 days post-procedure due to procedural complications
- Intracerebral hemorrhage (ICH) > 30 days post-procedure (Delayed ICH)
- Parent artery stenosis (per Core Lab)
- Device migration (per Core Lab)

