The incidence of complete aneurysm occlusion without significant parent artery stenosis ($\leq 50\%$) at 1 year post-procedure and without re-treatment of the target aneurysm (Primary Efficacy Endpoint) will be based on the Scale of Roy. Results will be based on the ITT population and will include the target aneurysm for each patient. The target aneurysm is defined as the largest aneurysm treated in the study procedure as identified by the core laboratory.

Results based on the ITT population will be presented in a table entitled *Overall Summary of the Post-Procedure Variables by Time*. The table will contain the point estimate and the confidence limit based on the exact Clopper-Pearson method. The supportive data for this table will be presented in a listing entitled *Post-Procedure Variables*. This listing will be sorted by patient number. Results based on the ICA population will be presented in a similar table and results based on the FAS population will be presented in a similar table.

Concomitant Medications

Concomitant medications refer to all medications taken from Day 0 thru study exit. *Antiplatelet medications were collected per their actual start date even if these were started prior to the study treatment (Day 0)*. *Prior medications* refer to all medications that were started and stopped prior to the first treatment with the Pipeline™ device with Shield Technology™ and will not be reported as concomitant.

The count and percent of subjects on anti-platelet medications will be summarized for 7 days pre-procedure, as well as for post procedure (were available) and presented in tables entitled *Summary of Dual Antiplatelet Therapy (DAPT)*. A summary of the concomitant medications will be presented in a table entitled *Summary of Concomitant Medications*, containing a clear declaration regarding the start date of the medication relative to the study procedure. The concomitant medications taken by the ITT population will be displayed in a listing entitled *Concomitant Medications*.

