7.9 Evaluation of Objectives

As previously described, the primary objective of this study is to assess the *outcomes* of the Pipeline™ Flex Embolization Device with Shield Technology™ in patients undergoing treatment for intracranial aneurysms in a large real-world, post-market setting. *Outcomes* will be assessed based on a series of standardized measurements recorded during the procedure and during the post-procedure follow-up period.

The Intent to Treat (ITT) will be considered the primary population, but not limited to, in the analysis of data for this study. When analyzing an outcome within a population, missing data will be reflected as the function of the denominator reported (xx.x% n/N) while the population number will remain constant. [i.e. ITT n=200 outcome Y (50%, 98/196)]

The pre-specified study endpoints and analysis listed here are the primary body of data that will be collected, analyzed, and summarized in a series of tables, lists, and graphs as part of the final report for this study. Other analysis will be conducted as part of the final report but these are the core set of analyses that will constitute the foundation of the clinical study report.

Primary endpoints:

Safety:

- Occurrence of major stroke in the territory supplied by the treated artery or neurological death post-procedure (1-year)

Effectiveness:

- Complete aneurysm occlusion (defined as Raymond-Roy grade 1) without significant parent artery stenosis ($\leq 50\%$) or retreatment of the target aneurysm post-procedure (1-year)

Secondary endpoints:

Safety:

- Occurrence of major stroke in the territory supplied by the treated artery or neurological death at 30 days post-procedure due to procedural complications
- Delayed intracerebral hemorrhage > 30 days post-procedure

Effectiveness:

- Device deployment success rate at the target site

Analysis for primary effectiveness endpoint interaction of site homogeneity and poolability testing will be conducted and reported.

Analysis of primary effectiveness endpoint by:

- Missing Data by Worst Case Scenario
- Aneurysm Location (with observed data)
- Aneurysm Location by Artery Segments (ITT population with observed data)
- By age (ITT and FAS population with observed data)

Analysis for primary effectiveness endpoint tipping point for incidence of complete target aneurysm occlusion at 1 year post procedure (ITT population)

CEC event of interest through 1 year will be reported for:

- GUSTO Bleeding
- Procedural:

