7.13.3 Post-Procedure Analyses

The first series of **Post-Procedure** analyses to be summarized will address the outcomes after the procedure. Within this series, there are 9 separate parameters:

- Aneurysm occlusion (Class 1: Complete obliteration, Class 2: Residual neck, or Class 3: Residual Aneurysm), derived from the post-procedure imaging adjudicated by Core Lab.
- Modified Rankin Scale (mRS); a multinomial endpoint that comes directly from the site reported case report form for evaluating the intra-patient over time and the change from baseline. The mRS will be scored for each patient by an evaluator at the clinical site. The mRS is a well-accepted and defined scoring system for measuring the degree of disability or dependence in the daily activities of people who have suffered a stroke using a multinomial ordinal scale:
 - 0 No symptoms at all
 - 1 No significant disability despite symptoms; able to carry out all usual duties and activities
 - 2 Slight disability; unable to carry out all previous activities, but able to look after own affairs without assistance

The mRS score at 1 year will be dichotomized (>2 vs. ≤ 2) and summarized using counts, percentages, and 2-sided 95% exact binomial confidence intervals.

- NIH Stroke Scale (NIHSS); a continuous endpoint that comes directly from the site reported clinical case report form for evaluating the intra-patient over time and the change from baseline. The NIHSS is a 15-item neurologic examination stroke scale used to evaluate the effect of acute cerebral infarction on the levels of consciousness, language, neglect, visual-field loss, extraocular movement, motor strength, ataxia, dysarthria, and sensory loss.
- Platelet reactivity testing, based on the VerifyNow, VASP, MEA, TEG, LTA testing reported as a percentage. A continuous endpoint that comes directly from the site reported clinical case report form.
- Change in antiplatelet therapy because of the platelet reactivity testing; a binary variable and comes directly from the site reported clinical case report form.
- Retreatment of the target aneurysm; a binary variable adjudicated by the imaging core laboratory. The recurrence of the aneurysm will be summarized using the percentage of subjects that experience aneurysm recurrence. Aneurysm recurrence is defined as an aneurysm that achieves complete occlusion at 6 months post-procedure, and then is no

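### SAP Section 6 ties the 50% effectiveness threshold to a measure without complete occlusion or freedom from retreatment, so it does not match the primary endpoint

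*SAP*

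**What the plan says.** **Endpoint.** SAP Section 5 and Section 7.9 define primary effectiveness as Raymond-Roy grade 1 occlusion without significant parent artery stenosis "or retreatment of the target aneurysm post-procedure (1-year"). Section 7.7 repeats the condition, "and without re-treatment of the target aneurysm (Primary Efficacy Endpoint) will be based on the Scale of Roy", for the target aneurysm of each ITT subject. The definitions table gives the same composite and names the source of its last component: "Retreatment: by the investigator reported events of retreatment".

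**Threshold.** Section 6 compares a shorter measure with its benchmark: "aneurysm occlusion without significant parent artery stenosis will be examined relative to an a priori threshold of 50" per cent. It mentions neither completeness nor retreatment. The sentence before it sets the safety threshold of 15% and restates both components of the primary safety endpoint.

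**Tipping point.** Section 7.9 introduces this as an analysis for the primary effectiveness endpoint, then describes it as a "tipping point for incidence of complete target aneurysm occlusion at 1 year post procedure (ITT population"), without stenosis or retreatment.

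**Images and retreatment.** Section 5 states: "At the investigator’s discretion, the target IA may be retreated at any time during the study"; Day 0 is not reset. The image-selection rule in Section 7.4 takes the last adjudicated image from day 141, subject to modality preferences, and does not mention retreatment. The occlusion row in Section 7.7 is "derived from the post-procedure imaging adjudicated by core lab", also with no rule for later images. Retreatment is a separate row.

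**Recurrence.** Section 7.13.3 says: "Aneurysm recurrence is defined as an aneurysm that achieves complete occlusion at 6 months post-procedure, and then is no" longer completely occluded on the core laboratory's 12-month reading. It has no clause for retreatment in between. The percentage of subjects retreated is presented alongside.

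**The concern.** The 50% figure is the only numeric effectiveness threshold in the SAP. A programmer who follows Section 6 as written would compute a variable that differs from the primary endpoint, and both omissions make it easier to meet. Retreatment is done to close the aneurysm, so on the literal measure a second intervention can turn a failure into a success. For occlusion the error can only run upward. For recurrence it can only run downward.

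The comparison has a use even without a formal test. SAP Section 3 says the results will be contrasted with Pipeline studies without Shield Technology and will inform, among other things, a US indication evaluation.

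**Working it through.** **1. Three courses for a target aneurysm, under each rule.** Stenosis is taken as 50% or less throughout, and all images as available.

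| Course | Primary endpoint (Sections 5, 7.7, 7.9) | Section 6, literal | Recurrence (7.13.3) |
|---|---|---|---|
| Complete at 6 and 12 months, no retreatment | Success | Success | No |
| Not complete at 6 months, retreated, complete at 12 months | Failure | Success | Not defined |
| Complete at 6 months, reopened, retreated, complete at 12 months | Failure | Success | No |

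The second and third rows are where Section 6 departs from the endpoint. The third is the gap in the recurrence rule. In both, the Roy-class row at 1 year would show class 1.

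**2. Size of the excess from omitting retreatment.** Excess = (share retreated) × (share of those then occluded with stenosis of 50% or less). The documents give neither factor. Assumed ranges are 2–8% and 50–100%.

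- Low: 0.02 × 0.50 = 0.01, or 1 point (2 of 200).
- High: 0.08 × 1.00 = 0.08, or 8 points (16 of 200).

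Dropping the word complete could add more if residual necks were counted as occluded. That part is not quantified here.

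**3. Where the reading against 50% can change.** The plan gives no sample-size or power figure for this comparison, so there is none to reproduce. Inputs: N = 200 (the SAP maximum, taken as fully observed) and the two-sided 95% Clopper-Pearson interval of Section 6. The lower limit for x successes is the 0.025 quantile of Beta(x, N − x + 1).

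| Successes of 200 | Rate | 95% interval |
|---|---|---|
| 110 | 55.0% | 47.8% to 62.0% |
| 114 | 57.0% | 49.8% to 64.0% |
| 115 | 57.5% | 50.3% to 64.4% |
| 120 | 60.0% | 52.9% to 66.8% |

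The lower limit first exceeds 50% at 115. The reading therefore flips only if the composite count is 114 or less and the count with rescued cases added is 115 or more.

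- With 2 rescued cases, the composite must be 113–114 (56.5–57.0%).
- With 16, it must be 99–114 (49.5–57.0%).
- Example: 110 on the composite does not clear 50%; 110 + 10 = 120 does.

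**4. Chance of clearing 50%**, P(X ≥ 115) for X binomial with N = 200 and success probability equal to the true composite rate plus the rescued share:

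| True composite rate | Rescued 0% | 2% | 5% | 8% |
|---|---|---|---|---|
| 50% | 0.020 | 0.068 | 0.262 | 0.587 |
| 55% | 0.262 | 0.473 | 0.787 | 0.953 |
| 60% | 0.787 | 0.916 | 0.988 | 0.999 |
| 70% | >0.999 | >0.999 | >0.999 | >0.999 |

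**5. Scale from the protocol.** Section 1.2.3 reports 78/106 = 73.6% complete occlusion without major stenosis at 180 days in an earlier Pipeline trial. The nearest count here is 147/200 = 73.5%, lower limit 66.8%. Adding 16 gives 163/200 = 81.5%, lower limit 75.4%. The estimate is inflated, but both clear 50%.

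**The case against.** The strongest reply is that Section 6 is shorthand. It also drops completeness and the numeric stenosis limit, no separate endpoint of occlusion without stenosis is defined anywhere, and the full composite stands in four places. That is probably how the sentence arose. It remains a mismatch in the one place that sets the number, next to a safety sentence that restates its endpoint's components.

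A reader might infer that a rescued aneurysm counts as a device success in this study. The documents do not support that. The defined primary endpoint fails any retreated target aneurysm, whatever a later image shows. The Roy-class rows describe anatomy by visit, and retreatment has its own row. The recurrence rule never labels an aneurysm a success, and the retreatment percentage is shown beside it. Nor can the tipping-point analysis be said to rest on occlusion alone, since its line opens by naming the primary effectiveness endpoint; its description is only incomplete.

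It is also fair that no decision hangs on 50%. Protocol Section 9.2 proposes no formal success criteria, and SAP Section 7.13.1 records no formal testing strategy. This lowers the severity. Separate reporting of retreatment does not remove the problem, because it does not show which retreated aneurysms were later counted as occluded.

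Finally, counting every retreatment as a recurrence would merge two outcomes that the protocol lists separately. That objection stands and shapes the fix.

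**Conclusion.** The mismatch is real. As worded, Section 6 applies its threshold to a more lenient measure than the primary effectiveness endpoint, and the recurrence rule misses an aneurysm that is retreated and closed again before the 12-month image.

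On the assumed retreatment and occlusion shares, the threshold measure would exceed the composite by 1 to 8 points. With 200 fully observed subjects this alters the reading against 50% only for a composite of about 50–57%. The earlier Pipeline occlusion figures in the protocol are higher: 73.6% at 180 days, 86.8% at one year (complete occlusion), and 75% at last visit in the registry (complete occlusion). They come from other populations and partly different definitions, so they show scale and are not a forecast.

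This should be fixed as an inconsistency. It does not threaten the defined primary analysis.

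**What to change.** - **Section 6:** apply the 50% threshold to the primary effectiveness endpoint as defined in Section 5: Roy class 1, stenosis of 50% or less, and no retreatment of the target aneurysm.
- **Section 7.9:** word the tipping-point analysis so that it names the same composite.
- **Section 7.13.3:** do not let a 12-month image taken after retreatment count as no recurrence. Either classify on the last image before retreatment, or show these subjects as a separate retreated category kept in the denominator.
- **Sections 7.7 and 7.13.3:** flag images taken after retreatment in the occlusion-by-visit tables.
- **At the same edit:** reconcile the source of the retreatment variable. The definitions table makes it investigator-reported; Section 7.13.3 has it adjudicated by the core laboratory.

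The cost is a few sentences and minor programming. Retreatment procedures are already recorded under the schedule of assessments, so no new data are needed. Some occlusion and recurrence figures may look slightly less favourable.
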